### 8.2 Analysis Data Definitions

#### 8.2.1 Baseline Definition

Unless otherwise stated, baseline for post-dose evaluations within each period is defined as the last observation recorded before the first study drug administration in each period. The last observation can be an unscheduled / repeated measurement.

## 8.2.2 Treatment/Subject Grouping

Label	Grouping
Study Drug	BMS-986251, Placebo
Treatment	Part A SAD cohorts: oral BMS-986251 Part B MAD cohorts: oral BMS-986251
Dose Level	Part A SAD cohorts: 2 mg, 6 mg, 15 mg, 30 mg, 60 mg Part B MAD cohorts: 3 mg QD

## 8.2.3 Common Variable Derivations

Variable	Dataset	Definition/Calculation
Change from Baseline	All	Post-dose Observation minus Baseline Observation
Percent Change from Baseline	All	Post-dose Observation minus Baseline Observation then divided by Baseline Observation
Analysis Period	All	Interval of time during which treatment is constant.
Duration	AE	Stop date/time minus start date/time plus 1, presented in dd:hh:mm.

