8.4.1.1 Part A – SAD in Healthy Volunteers

In the morning of Day 1, after fasting for at least 10 hours, each subject will receive a single oral dose of BMS-986251 or placebo at approximately 9:00 AM as an oral solution of up to a planned volume of 6 mL, depending on the dose level. The medication time is provided as an indication only (for scheduling purposes).

Subjects enrolled in the BA/FE cohort will receive a second single oral dose of BMS-986251 at approximately 9:00 AM on the morning of Day 1 of Period 2, as an oral suspension (under development; representative for the solid dosage form to be used in Part C), after a 10-hour overnight fast. These subjects will receive a third single oral dose of BMS-986251 at approximately 9:00 AM on the morning of Day 1 of Period 3, as an oral suspension, 30 minutes after start of consumption of a high-fat breakfast. The high-fat breakfast (see [Appendix 5](#)) has to be consumed completely in 20 minutes. The exact time of start and end of breakfast and the exact time of dosing will be recorded in the eCRF. Washout between single dose administrations will be at least 2 weeks, based on an anticipated terminal half-life of BMS-986251 of approximately 40 hours.

In all study periods, at the time of dosing, a total of 240 mL of water will be administered to the subjects in all cohorts along with his/her dose of study drug. The time of BMS-986251/placebo administration will be called “0” hour. The exact time of dosing will be recorded in the eCRF. Subjects will remain fasted until at least 4 hours after administration. Water is allowed during fasting, except for 2 hours before and 1 hour after administration.

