8.4.1.2 Part B – MAD in Healthy Volunteers

In the morning of Days 1-14, each subject will receive a single oral dose of BMS-986251 or placebo at approximately 9:00 AM as an oral solution of up to a planned volume of 6 mL, depending on the dose level. The medication time is provided as an indication only (for scheduling purposes). On Days 1 and 14, subjects will fast for at least 10 hours prior to dosing. At the time of dosing, 240 mL of water will be administered to the subject along with his/her dose of study drug. The time of first dose administration will be called “0” hour; all other time points will be relative to time “0”. The exact time of dosing will be recorded in the eCRF. On Days 1 and 14, subjects will remain fasted until at least 4 hours after administration. Water is allowed during fasting, except for 2 hours before and 1 hour after administration.

On Days 2 to 13, BMS-986251 or placebo will be administered in the fasted state. After dosing, subjects will continue their fast until breakfast. The breakfast will be provided approximately 2 hours after dosing. Water is allowed during fasting, except for 2 hours before and 1 hour after administration.

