## 8.4.3 Hypothesis Testing

No formal hypothesis testing will be done.

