### 17.1.1 Adverse Events

An AE is defined as any new untoward medical occurrence or worsening of a preexisting medical condition in a clinical investigation participant that does not necessarily have a causal relationship with treatment. AE summaries will include only TEAEs. TEAEs are those which occur after the first dose of study drug. All TEAE summaries will be presented alphabetically by system organ class, with preferred terms sorted in decreasing order of frequency within each system organ class based on MedDRA version 21.0.

TEAEs occurring following dosing in a specific period but before dosing in the following period will be attributed to that specific period. If the time is missing for an AE on a dosing day then the AE will be attributed to the treatment given on that day.

The following missing data will be imputed (for calculations only) as defined:

- Missing AE start and / or end times for the calculation of onset and duration will be assumed to be at 00:01 for a start time and 23:59 for end times
- Missing AE severity or relationship will be left as missing
- Missing AE start times for the determination of treatment emergence will be assumed to occur after treatment unless partial date documents the AE as happening prior to treatment
- Missing AE start times for the determination of treatment assignment will be assumed to occur after treatment on the recorded date one minute after dosing
- Missing AE start date will be assumed to be after treatment for the determination of TEAE, but will not be attributed to a specific treatment in studies with multiple treatments.

A summary of the number and percentage of subjects reporting TEAEs, serious AEs (SAEs), who discontinue study drug due to a TEAE, and will be presented by treatment and overall.

A summary of the number and percentage of subjects reporting each TEAE will be presented by treatment and overall. Counting will be done by subject only, not by event; subjects will only be counted once within each body system or preferred term.

A summary of the number and percentage of subjects reporting each TEAE will be presented by relationship to study drug (as recorded on the eCRF) and by treatment and overall. Subjects with multiple events within a particular system organ class (SOC) or preferred term will be counted as related unless no events were related in that SOC/preferred term.

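### SAP adverse-event timing: the 1 added to duration has no unit, and a missing start time is 00:01 for onset and duration but after the dose for treatment emergence and assignment

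*SAP*

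**What the plan says.** SAP 8.2.3 (Common Variable Derivations) gives the duration of an AE as "Stop date/time minus start date/time plus 1, presented in dd:hh:mm". The display runs to the minute, and the unit of the 1 is not stated.

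SAP 17.1.1 (Adverse Events) handles a missing start time differently for each purpose:

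- For onset and duration, missing times "will be assumed to be at 00:01 for a start time and 23:59 for end times".
- For TEAE status: "Missing AE start times for the determination of treatment emergence will be assumed to occur after treatment", with an exception only where a partial date documents an earlier start.
- For treatment assignment, the event "will be assumed to occur after treatment on the recorded date one minute after dosing".

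The same section states that "TEAEs are those which occur after the first dose of study drug".

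On the clock time of dosing, Protocol 8.4.1.1 (Part A) says that "each subject will receive a single oral dose of BMS-986251 or placebo at approximately 9:00 AM". Protocol 8.4.1.2 (Part B) says "In the morning of Days 1-14, each subject will receive a single oral dose of BMS-986251 or placebo at approximately 9:00 AM". Both sections describe this time as indicative, for scheduling.

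**The concern.** There are two separate problems.

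Adding 1 is a convention for counting whole calendar days inclusively. When both ends carry a clock time, elapsed time is the plain difference and nothing needs adding. Because the SAP attaches a 1 with no unit to a date/time difference, a programmer has to guess, and the plausible guesses differ by a factor of 1,440 (a day against a minute).

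The imputation rules also give one event two start times. For a Day 1 event with no recorded start time, the emergence and assignment rules put it after the dose, while the onset and duration rule puts it just after midnight, before the dose. The derived record then contradicts the SAP's own TEAE definition.

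At stake are derived values in ADAE, which SAP 8.2.4.1 classes as critical data. AE reporting here is descriptive and the study is small: SAP 7.1 reports 36 subjects dosed in Part A and 2 in Part B. Readers of such a study look at single events and when they fell relative to the dose.

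**Working it through.** The documents give no figure to reproduce on this point. The check applies the rules literally.

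**Inputs.** Duration rule: SAP 8.2.3. Imputed times 00:01 and 23:59, and dose time + 1 minute: SAP 17.1.1. Dose at 09:00: Protocol 8.4.1.1 and 8.4.1.2, used as an assumption because the time is indicative; onset figures shift one for one with the actual dose time.

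**1. Size of the added 1, complete times.** Reported duration = stop − start + 1 unit, shown as dd:hh:mm.

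| True length | +1 minute | +1 hour | +1 day | Ratio if a day |
|---|---|---|---|---|
| 30 min | 00:00:31 | 00:01:30 | 01:00:30 | 24.5/0.5 = 49 |
| 2 h | 00:02:01 | 00:03:00 | 01:02:00 | 26/2 = 13 |
| 3 h | 00:03:01 | 00:04:00 | 01:03:00 | 27/3 = 9 |
| 5 days | 05:00:01 | 05:01:00 | 06:00:00 | 6/5 = 1.2 |

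Read as a day, the rule distorts short events most. Read as a minute, it changes even the 30-minute event by only 31/30 = 1.03.

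**2. Onset, Day 1 event with no start time.**

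- Onset rule: 00:01 − 09:00 = −8 h 59 min.
- Assignment rule: 09:01 − 09:00 = +1 min.

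The event is counted as a TEAE but has a derived onset before the first dose.

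**3. Duration of the same event, before any added 1.**

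- Stop recorded at 10:30: 10:30 − 00:01 = 10 h 29 min. The most that can follow the dose is 10:30 − 09:00 = 1 h 30 min. A 09:01 start gives 1 h 29 min.
- Stop also missing: 23:59 − 00:01 = 23 h 58 min (01:23:58 if a day is added). The most that can follow the dose on that date is 24:00 − 09:00 = 15 h. A 09:01 start gives 14 h 58 min.

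This overstatement does not depend on the unit of the added 1.

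**4. Later dosing days in Part B.** On Day 5, for example, 00:01 is again 8 h 59 min before that day's dose, but 3 d 15 h 1 min after the first dose. The conflict with the TEAE definition therefore arises on Day 1 only.

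**5. Does dose + 1 minute always work as the single start?** No. A Day 1 event with a recorded stop at 08:00 would get 08:00 − 09:01 = −1 h 1 min. A Part B Day 5 event stopping at 07:00 would get 07:00 − 09:01 = −2 h 1 min. With 00:01 these are 7 h 59 min and 6 h 59 min. The single-start rule needs an exception for events known to precede the dose.

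**The case against.** **The unit may be a minute.** The display resolves to minutes, so an inclusive minute is a natural reading. A reader might infer that every AE duration in the report will be a day too long; the SAP does not say so. What stands is that the unit is missing. Double programming of ADAE does not settle it, since two programmers may choose differently or choose the same wrong unit.

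**Nothing that is tabulated uses these variables.** This stands. The primary safety endpoints in SAP 5.1.1 are subject counts. AE Tables 14.4.1.1 to 14.4.1.4 in SAP Appendix 4 are organised by system organ class, preferred term, relationship and severity, and SAP 17.1.1 counts by subject. Because emergence and assignment have their own post-dose rules, the 00:01 rule does not reach those counts.

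**Impossible times may never be displayed.** A reader might infer that pre-dose onsets will appear in the AE listing and pass into the narratives. The documents do not show this. SAP 17.1.1 imputes for calculations only, SAP 8.1.1 lists data at their original precision, and the shells that would show whether a listing carries derived onset or duration are in a separate document. Appendix 4 only reserves a number for narratives. It remains a risk, since SAP 8.2.3 does intend duration to be presented.

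**Relatedness is not affected.** A reader might infer that a false onset would bias causality. Protocol Appendix 2 leaves causality to a physician, and SAP 17.1.1 uses it as recorded on the eCRF. No rule feeds derived onset into it.

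**Separate rules can be deliberate, and the trigger is narrow.** Assuming an undated time to be post-dose is a reasonable conservative rule for counting TEAEs, and 00:01 to 23:59 gives an upper bound on duration that is never negative. Neither explains a pre-dose onset for an event declared treatment-emergent. The conflict needs a missing start time on a dosing day. Part A and Part B subjects were confined to the unit on those days, so such gaps may be few.

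**Conclusion.** The point holds as two limited defects in derivation rules.

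The duration formula is underspecified. Its effect runs from trivial, if the 1 is a minute, to 24 h on every event, if it is a day.

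The missing-time rules are inconsistent whatever that unit is. Assuming a 09:00 dose, a Day 1 event with no start time is a TEAE with a derived onset of −8 h 59 min. With both times missing it has a derived duration of 23 h 58 min, against at most about 15 h after the dose.

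The effect is confined to derived onset and duration in ADAE and in any listing that shows them. How many events are affected cannot be known from the documents. This is a minor correction, worth making because it is cheap and the dataset is one the SAP calls critical.

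**What to change.** In SAP 8.2.3, define AE duration as stop date/time minus start date/time, with no added 1, whenever both times are recorded or imputed. Use an inclusive day count only for durations reported in whole days from dates alone, and say so.

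In SAP 17.1.1, for an event dated on a dosing day with a missing start time, use one imputed start, dose time + 1 minute, for onset, duration, emergence and assignment. Make one exception: if a recorded stop time or other information places the event before that day's dose, keep 00:01 and classify the event as starting before that dose, and as not treatment-emergent if that is the first dose.

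The cost is about two lines of SAP text and one derivation in ADAE. Using a single start leaves the subject counts as they are. Only the exception could alter one: a Day 1 event with no start time that ended before the first dose would leave the TEAE count, whereas the present text exempts only events whose partial date shows an earlier start.

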## 8.2.4 QC

The analysis datasets and the TFLs will be quality control (QC)'d according to the PRA EDS QC plan that is developed according to the EDSREP 009 SOP.

### 8.2.4.1 Critical Data

The QC plan requires datasets be classified as critical or non-critical. As key objectives of this study are to characterize the pharmacokinetics and assess safety and tolerability, the datasets considered critical are subject level, pharmacokinetic, and adverse events (ADSL, ADPC, ADPP, and ADAE). As these are related to the primary objectives these datasets will be double programmed per the QC Plan.

## 8.2.5 ADaM Datasets and Metadata

The analysis datasets will be generated in accordance with Clinical Data Interchange Standard Consortium (CDISC) Analysis Data Model (ADaM) Version 2.1.

ADaM compliant datasets will be delivered to the sponsor. A define.xml file version 2 with the corresponding metadata will be included. Analysis results metadata are excluded.

## 8.3 Software

The statistical analysis and reporting will be done using SAS® for Windows™ Version 9.4 or higher (SAS Institute, Inc.).

PK parameter calculations will primarily be done using Phoenix® WinNonlin® (WNL) Version 6.3 or higher (Pharsight, Inc.). Additional PK computations may be performed in SAS®.

## 8.4 Statistical Methods

### 8.4.1 Statistical Outlier Determination

No statistical outlier analysis is planned.

## 8.4.2 Predetermined Covariates and Prognostic Factors

There are no predetermined covariates or prognostic factors.

## 8.4.3 Hypothesis Testing

No formal hypothesis testing will be done.

## 9.0 Analysis Sets

Analyses	Enrolled	Safety	PK	PD
Disposition	✓			
Demographics and Baseline Characteristics		✓		
Safety Assessments		✓		
PK Concentrations			✓	
PK Parameters			✓	
PD Concentrations				✓

### 9.1 Enrolled

The Enrolled analysis set will consist of all subjects who signed informed consent. This analysis set will be used for disposition summaries.

### 9.2 Safety

The Safety analysis set will consist of subjects who receive at least one dose of study drug. This set will be used for disposition summaries, baseline characteristic summaries, and safety summaries.

### 9.3 Pharmacokinetic

The PK analysis set will consist of all subjects who receive at least 1 dose of BMS-986251 and have sufficient concentration-time data to calculate a valid Cmax and AUC(0-T).

### 9.4 Pharmacodynamic

All subjects who receive at least 1 dose of BMS-986251 or placebo and have any available data for the PD assessments.

## 10.0 Subject Disposition

The number of subjects in each analysis set will be presented. The number and percentage of subjects who withdrew from the study prematurely and a breakdown of the corresponding reasons for withdrawal will also be presented. Percentages will be based on the total number of subjects in the analysis set.

## 11.0 Protocol Deviations

Protocol deviations will be collected and entered into the Clinical Trial Management System (CTMS) per clinical monitoring Standard Operating Procedures. From CTMS, protocol deviations will be pulled into SDTM. All protocol deviation data will be listed by subject.

## 12.0 Demographic and Baseline Characteristics

### 12.1 Demographics

Subject demographics will be summarized descriptively for all subjects by analysis set and treatment group. The summary will include the subjects' age (in years), sex, race, ethnicity, weight (in kg), height (in cm), and body mass index (BMI) (in kg/m^2). Any measurements will be included from assessments performed during the Screening Visit. Demographics will be summarized for the Safety, PK and PD analysis sets.

All demographic data, as collected during the screening visit and Day -1, will be listed by subject.

### 12.2 Medical History

Medical history will be listed by subject. Medical history data will be coded according to the latest Medical Dictionary for Regulatory Activities (MedDRA) version 21.0.

### 12.3 Other Baseline Characteristics

Substance use (tobacco and alcohol) will be listed.

The results of drug and alcohol screen at screening and at pre-treatment will be listed.

The results of pregnancy tests at screening and at pre-treatment will be listed, the results for follicle stimulating hormone (FSH) tests at screening will be listed.

The results of serology, including hepatitis B surface antigen (HBsAg), anti-hepatitis C virus (HCV) antibodies or anti-human immunodeficiency virus (HIV) 1 and 2 antibodies will be listed.

The results of Quantiferon Gold test® for tuberculosis (TB) at screening will be listed.

Non-compliance to in- or exclusion criteria (if any) will be listed.

## 13.0 Prior and Concomitant Medications

Prior and concomitant medications, categorized by medication group and subgroup according to the World Health Organization (WHO) Drug Dictionary Version 2018MAR01+HD (Enhanced+Herbal) B3, will be listed by subject. Medications with an end date prior to the first dose of study drug will be considered prior medications and will be identified in the listing. If a partial date allows a medication to be considered concomitant it will be categorized as such.

## 14.0 Treatment Compliance and Exposure

The number of subjects receiving each dose of study drug will be summarized.

All study drug administration data will be listed by subject. If applicable, date and time and food and fluid intake and comments will be listed.

## 15.0 Pharmacokinetic Analyses

The PK summaries described in this section will be created using the PK analysis set.

### 15.1 Pharmacokinetic Variables

#### 15.1.1 Plasma Variables

##### 15.1.1.1 Concentrations

- Plasma concentration of BMS-986251

### 15.1.1.2 Parameters

PK Parameters for BMS-986251 as defined Table 4.

**Table 4 Plasma BMS-986251 PK Parameters- Part A (SAD Part)**

Parameter	SAD Part	MAD Part Day 1*	Description	SAS Programming Notes
Cmax	X	X	Maximum plasma concentration. Observed peak analyte concentration obtained directly from the experimental data without interpolation, expressed in concentration units	Cmax from WNL
Tmax	X	X	Time to maximum plasma concentration. First observed time to reach peak analyte concentration obtained directly from the experimental data without interpolation, expressed in time units.	Tmax from WNL
AUC(0-T)	X	X	Area under the concentration-time curve (time 0 to time of last quantifiable concentration).	AUClast from WNL
AUC(INF)	X	X	Area under the plasma concentration-time curve (time 0 to infinity). A valid half-life is required to retain this parameter.	AUCINF_obs from WNL If T-HALF is present.
AUC%Extrap	X	X	Percentage of the AUC(INF) that is extrapolated.	AUC_%Extrap_obs from WNL– Listed only
T-HALF	X	X	Terminal phase half-life expressed in time units. A valid Lz is required to retain.	HL_Lambda_z from WNL
Lz	X	X	Terminal phase rate constant calculated by the WinNonlin generated best fit linear regression of the terminal log-linear portion of the concentration vs. time curve. Linear regression of at least 3 points and an adjusted R2 > 0.80 are required to retain.	Lambda_z from WNL.
CL/F	X	X	Apparent clearance	CL_F_obs from WNL
Vd/F	X	X	Apparent volume of distribution at terminal phase	Vz_F_obs from WNL
Adj R 	X	X	Adjusted R  value of terminal elimination phase	Rsquared adjusted from WNL – Listed only

Parameter	SAD Part	MAD Part Day 1*	Description	SAS Programming Notes
Lz_Start	X	X	The time point starting the log-linear elimination phase defining their terminal half-life	Lambda_z_lower from WNL – Listed only
Lz_End	X	X	The time point ending the log-linear elimination phase defining the terminal half-life	Lambda_z_upper from WNL – Listed only
Lz_N	X	X	Number of time points in the log-linear elimination phase defining the terminal half-life	No_points_lambda_z from WNL – Listed only

Note: AUCs will be calculated using linear up / log down, expressed in units of concentration x time.

\* There are only 2 subjects in cohort B1 who have been dosed till Day 10. PK parameters will be calculated for Part B (MAD part) Day 1 if feasible.

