8.5.3 Pharmacokinetics

Pharmacokinetic variables will be the plasma concentrations and urine concentrations (Part A and B only) of BMS-986251 and derived PK parameters. The PK parameters to be assessed for BMS-986251 include but are not limited to the parameters given below. Some of the listed parameters may only be calculated for specific parts of the study; this includes the assessment of urinary excretion of parent compound and metabolites in urine, which may be limited to the higher dosed cohorts in Part A and B. The relevant PK parameters to be calculated for each study part and study day are listed in Section 9.3.1.

C_{pre}	Pre-dose plasma concentration
C_{max}	Maximum observed plasma concentration
t_{max}	Time of maximum observed plasma concentration
AUC_{0-t}	Area under the plasma concentration-time curve from time zero to time of last quantifiable concentration
AUC_{0-inf}	Area under the plasma concentration-time curve from time zero extrapolated to infinite time
AUC_{0-24}	Area under the concentration-time curve over 24 hours (one dosing interval)
$AR_{C_{max}}$	Accumulation ratio: ratio of C_{max} following last dose (Day 14) to C_{max} following first dose (Day 1)
$AR_{AUC_{0-24}}$	Accumulation ratio: ratio of AUC_{0-24} following last dose (Day 14) to AUC_{0-24} following first dose (Day 1)
k_{el}	Terminal elimination rate constant
$t_{1/2}$	Terminal elimination half-life, calculated as $0.693/k_{el}$
CL/F	Apparent (oral) clearance, calculated as dose/ AUC_{0-inf} for single dose (Part A, Day 1) or dose/ AUC_{0-24} for multiple dose (Part B and C, Day 14)
V_z/F	Apparent volume of distribution at terminal phase
Ae_t	Cumulative urinary excretion (of the unchanged drug) (Part A and B only)
$Fe_{urine}\%$	Amount excreted unchanged in urine (% of dose) (Part A and B only)
CL_R	Renal clearance (Part A and B only)

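### SAP Table 4 makes Lz, T-HALF and AUC(INF) depend on an acceptable terminal fit but states no such condition for CL/F and Vd/F, which use the same slope

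*SAP*

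**What the plan says.** SAP section 15.1.1.2, Table 4, has a Description column and a SAS Programming Notes column. Together they set up a chain:

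- **Lz:** "Linear regression of at least 3 points and an adjusted R2 > 0.80 are required to retain".
- **T-HALF:** "A valid Lz is required to retain".
- **AUC(INF):** "A valid half-life is required to retain this parameter", repeated in the programming note as "AUCINF_obs from WNL If T-HALF is present".
- **CL/F:** described as apparent clearance, note "CL_F_obs from WNL". Neither column has a condition.
- **Vd/F:** described as the terminal-phase volume, note "Vz_F_obs from WNL". Neither column has a condition.
- **AUC%Extrap:** "AUC_%Extrap_obs from WNL– Listed only". It has no condition either, but it stays out of the summaries.

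The CL/F and Vd/F rows do not carry the listed-only tag, so they fall under section 15.2.2, which summarises the calculated PK parameters by treatment. Protocol 8.5.3 gives the definition "Apparent (oral) clearance, calculated as dose" over AUC from zero to infinity for a single dose. Protocol 9.3.1 names CL/F and Vz/F among the Part A parameters under the primary PK endpoints.

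**The concern.** CL/F after a single dose is the dose divided by AUC(INF), and Vd/F divides that again by Lz. If Lz is not good enough to support AUC(INF), it is not good enough to support either of them. Yet the table withholds AUC(INF) and says nothing about the other two.

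Two things are at stake. First, in one summary table CL/F and Vd/F could rest on more subjects than AUC(INF), so the reported clearance would not correspond to the reported exposure. Second, rejected fits are most likely where few quantifiable terminal samples remain, that is at the lowest dose. There a slope that is too shallow raises AUC(INF) and lowers CL/F. With about six active subjects per cohort, one poor value can move a cohort summary.

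**Working it through.** **1. Dependence on the slope.**

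- AUC(INF) = AUC(0-T) + Clast/Lz
- CL/F = Dose/AUC(INF)
- Vd/F = Dose/(Lz × AUC(INF))

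A rejected Lz therefore enters both CL/F and Vd/F.

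**2. Does another passage close the gap?**

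- SAP 9.3: the PK set needs only a valid Cmax and AUC(0-T), so a subject with a rejected Lz stays in it.
- SAP 15.2.2: repeats the 3-point minimum and excludes the Cmax point, but adds no condition for CL/F or Vd/F.
- Protocol 9.4.3: limits summary statistics to subjects with adequate PK profiles. The term is undefined and works by subject. The SAP repeats it only for urine parameters (15.2.4), and SAP 3.0 says the SAP supersedes the protocol's statistical considerations.
- SAP 7.1: the summary tables named for Part B do not include PK, so the effect on summaries concerns Part A. Any Part B Day 1 values would appear in listings.

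**3. How much of AUC(INF) rests on the slope.** For a mono-exponential decline with the anticipated 40 h half-life (Protocol 8.1.1), the share beyond the last quantifiable time T is 0.5^(T/40):

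| T (h) | Extrapolated share |
|---|---|
| 240 | 1.6% |
| 144 | 8.2% |
| 72 | 28.7% |
| 24 | 66% |

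**4. What the assay limit does.** Neither the limit nor the residual error is in the documents, so both are assumed. Concentration falls to a fraction f of Cmax after about 40 × log2(1/f) hours:

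- f = 2%: 40 × 5.64 = 226 h
- f = 20%: 40 × 2.32 = 93 h
- f = 40%: 40 × 1.32 = 53 h

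If Cmax is proportional to dose, a limit at 20% or 40% of the 2 mg Cmax is 6.7% or 13.3% of the 6 mg Cmax (multiply by 2/6). These are reached at about 156 h and 116 h. Truncation therefore eases quickly as dose rises.

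**5. Simulation of the Part A sampling times.** Assumptions: one compartment, 40 h half-life, 30% between-subject variability, 6 active per cohort, linear-up/log-down AUC, best adjusted-R2 terminal fit excluding Cmax.

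- Limit 2% of the 2 mg Cmax, residual error up to 20%: almost no fit fails and nothing changes.
- Limit 20-40% of the 2 mg Cmax, error 20%: 16-42% of 2 mg profiles fail. The chance of at least one failure among six is 1 − 0.84^6 = 0.65 to 1 − 0.58^6 = 0.96 (simulated 66-96%). Failed profiles have median CL/F 12-18% below truth.

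| Limit, % of 2 mg Cmax | Geometric mean CL/F / truth, kept | Dropped |
|---|---|---|
| 20% | 0.94 | 0.96 |
| 40% | 0.84 | 0.94 |

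**6. By dose.** A separate run of the same model at 20% error gave failure rates, at the 20% and 40% limits, of 17% and 44% at 2 mg, 0.8% and 6.6% at 6 mg, and at most 0.5% at 15 and 30 mg. From 6 mg upward, kept and dropped geometric means differ by at most 0.005. At 30% error up to 27% fail at 6 mg, with 0.92 kept against 0.94 dropped.

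**7. Spread in rejected fits.** A third simulation, without between-subject variability and with the limit at 30% of Cmax, rejected 3%, 35% and 58% of fits at 10%, 20% and 30% error. The 5th to 95th percentile of CL/F over truth in rejected fits was 0.67-1.09 at 10% error and 0.33-1.21 at 30%. Vd/F was centred near truth (median 1.03-1.05) but widely spread (0.70-1.55 at 30% error).

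**The case against.** The strongest reply is that Table 4 does not order anyone to keep a rejected value. The programming notes for Lz and T-HALF are as bare as those for CL/F and Vd/F, and their conditions sit in the Description column. A bare note therefore names the WinNonlin source variable and is not a retention rule. A programmer who follows the protocol definition would have no AUC(INF) to divide by and would set CL/F to missing. The SAP is to be read with the protocol and identifies no departure here, and the separate table shells might settle the matter. This stands as far as it goes: retention is by omission. But CL/F and Vd/F have no condition in either column, and the note points to a ready-made WinNonlin output, so the text leaves the choice open.

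It is also fair that little depends on it. The dose-proportionality analysis in SAP 15.2.3.1 uses Cmax, AUC(0-T) and the already conditioned AUC(INF). CL/F enters no model, SAP 8.4.3 plans no formal hypothesis testing, and the study had already been terminated when the SAP was written. Adjusted R2, the fit range, the number of points and AUC%Extrap are all listed, so a poor fit can be traced.

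A reader might infer that the CL/F and Vd/F summaries do contain values the plan itself calls invalid. The documents do not support that: they report no rejected fit, and the validity wording is attached to Lz and the half-life, not to CL/F or Vd/F.

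**Conclusion.** The gap is real and textual. Three parameters are conditioned on the terminal fit, while two that depend on the same slope are not, and no other SAP passage closes it. Its effect on results is conditional. It needs at least one rejected fit in Part A and a program that passes the WinNonlin value through.

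Under the assumed limits of 20-40% of the 2 mg Cmax with 20% error, keeping rejected fits lowers the 2 mg geometric mean CL/F by 0.02 (0.96 − 0.94) to 0.10 (0.94 − 0.84) of the true value. There is almost no effect from 6 mg upward, and none anywhere if the limit is low and profiles run to 240 h. Dropping the rejected fits does not remove all bias: the 0.94 at the 40% limit is what truncation leaves behind.

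It would be tempting to say that the trial will show a false dose-dependence of clearance, or that a primary analysis is compromised. Neither follows. The first needs an assay limit that the documents do not give, and the formal assessment of proportionality does not use CL/F. This is a minor consistency correction.

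**What to change.** In Table 4, add to the CL/F and Vd/F rows the same requirement that the AUC(INF) row already has, namely that the value is retained only if T-HALF is present. CL/F, Vd/F, AUC(INF) and T-HALF are then summarised on the same subjects. In the listings, flag AUC%Extrap and any CL/F or Vd/F that comes from a rejected fit, so that nothing is lost from view.

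The cost is a few words in the SAP and one condition in the program. The downside is a smaller n for CL/F and Vd/F in any cohort with rejected fits.
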